Patients who initiated nirmatrelvir/ritonavir treatment between 11 February 2022 and 31 August 2022 will be included in this study. For the purposes of analysis, the index date for an individual patient is defined as the date of initiating nirmatrelvir/ritonavir treatment. The baseline period for an individual patient is defined as the period from the first day of hospitalization to the day prior to the index date to capture the patient's baseline clinical characteristics, medical history, and comorbidity. The observation period for an individual patient is defined as the period from initiation of nirmatrelvir/ritonavir (i.e., index date) until discharge from hospital, death, or a maximum of 28 days after the last dose of nirmatrelvir/ritonavir, whichever comes first.

The study data cut-off date will be 02 October 2022. Each patient will be included in the study only once. If the patient initiated nirmatrelvir/ritonavir treatment more than once between 11 February 2022 and 31 August 2022, only the first treatment course will be included for analysis.

Population

Study population will consist of patients who initiated treatment with nirmatrelvir/ritonavir within the period from 11 February 2022 to 31 August 2022 during hospitalization. Approximately 1000 patients are planned to be included in the study. Eligible patients must meet the following inclusion criteria and none of the exclusion criteria:

Inclusion criteria

- Chinese patients aged ≥ 18 years on index date
- Patients initiated and took at least one dose of nirmatrelvir/ritonavir between 11 February 2022 and 31 August 2022 during hospitalization
- Patients had documented confirmed symptomatic COVID-19 with positive SARS-CoV-2 test in any specimen collected prior to or at initiation of nirmatrelvir/ritonavir
- Evidence of a personally signed and dated informed consent document (ICD) indicating that the patient (or a legally acceptable representative) has been informed of all pertinent aspects of the study if requested by study sites.

Exclusion criteria

- Patients participated in any interventional COVID-19 trials during the study period

Variables

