9.2. Setting

Study population will consist of patients who initiated treatment with nirmatrelvir/ritonavir between 11 February 2022 and 31 August 2022 during hospitalization. Approximately 1000 patients are planned to be included in the study. Eligible patients must meet the following inclusion criteria and none of the exclusion criteria:

Inclusion criteria

- Chinese patients aged \geq 18 years on index date
- Patients initiated and took at least one dose of nirmatrelvir/ritonavir between 11 February 2022 and 31 August 2022 during hospitalization
- Patients had documented confirmed symptomatic COVID-19 with positive SARS-CoV-2 test in any specimen collected prior to or at initiation of nirmatrelvir/ritonavir
- Evidence of a personally signed and dated ICD indicating that the patient (or a legally acceptable representative) has been informed of all pertinent aspects of the study if requested by study sites.

Exclusion criteria

- Patients participated in any interventional COVID-19 trials during the study period.

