9.3. Variables

This study will retrospectively abstract individual-level data from the HIS and LIS, which include electronic/paper medical records, prescription files, and laboratory testing results. Data for baseline variables will be abstracted from the baseline period. Data for primary and secondary endpoint variables will be abstracted from the observation period.

Table 1. List of variables and operational definitions

Variable	Role	Data source(s)	Operational definition
Age	Demographics /subgroup identifier	HIS	Age on index date. Age = Year of index date - Birth year See section 9.3.1 Risk factors for more detail.
Sex	Demographics	HIS	As recorded in medical record (male or female).
BMI	Baseline clinical characteristics / subgroup identifier	HIS	As recorded in medical record for individual height and weight or BMI. BMI = weight (kg) / [height (m)] ² . According to the WHO standard, four categories of BMI (kg/m ²) are underweight (<18.5), normal weight (18.5 ≤ BMI < 25.0), pre-obesity (25.0 ≤ BMI < 30.0) and obesity (≥ 30.0). ²¹ According to China guideline, four categories of BMI (kg/m ²) are underweight (<18.5), normal weight (18.5 ≤ BMI < 24.0), pre-obesity (24.0 ≤ BMI < 28.0) and obesity (≥ 28.0). ²² The assessment on or closest to the index date will be used. Both BMI categorizations will be used for analysis. See section 9.3.1 Risk factors for more detail.

PFIZER CONFIDENTIAL

090177e19c018db1\Approved\Approved On: 07-Dec-2022 08:12 (GMT)

Table 1. List of variables and operational definitions

Variable	Role	Data source(s)	Operational definition
Smoking status	Baseline clinical characteristics / subgroup identifier	HIS	As recorded in medical record. See section 9.3.1 Risk factors for more detail.
COVID-19 severity at baseline	Baseline clinical characteristics / subgroup identifier	HIS	COVID-19 severity will be categorized into four levels. Apart from categories of severity level, severity scale used and the relevant parameters used for severity assessment will also be abstracted from medical records. See section 9.3.2 COVID-19 severity for categorization and parameters in detail. The assessment of severity level on or closest to the index date will be used.

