9.3.1. Risk factors

Risk factors (as defined in the nirmatrelvir/ritonavir label²⁶) are as follows:

- Being overweight/obesity (e.g., BMI > 25 kg/m²)
- Older age (e.g., age \geq 60 years)
- Current smokers
- Immunosuppressive disease or immunosuppressive treatment

- Comorbidity
 - Chronic kidney disease
 - Diabetes
 - Cardiovascular disease (including congenital heart disease) or hypertension
 - Chronic lung diseases (e.g., chronic obstructive pulmonary disease, asthma [moderate-to-severe], interstitial lung disease, cystic fibrosis, and pulmonary hypertension)
 - Sickle cell disease
 - Neurodevelopmental disorders (e.g., cerebral palsy, Down's syndrome) or other conditions that confer medical complexity (e.g., genetic or metabolic syndromes, and severe congenital anomalies)
 - Active cancer
 - Medical-related technological dependence not related to COVID-19 (e.g., tracheotomy, gastrostomy, or positive pressure ventilation)

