9.7.1. Analysis sets

- Full Analysis Set (FAS):

The FAS will include all patients who meet the inclusion criteria and do not meet the exclusion criteria described in section 9.2.

- Safety Analysis Set (SAS):

The SAS will include all patients from FAS.

- Effectiveness Analysis Set 1 (EAS1):

The EAS1 will include all patients from FAS who had at least one of the effectiveness variables collected and had the latest positive SARS-CoV-2 test result within 5 days prior to administration initiation.

- Effectiveness Analysis Set (EAS):

The EAS is a subset of EAS1 and will include patients who had mild or moderate COVID-19 illness at baseline and had at least one risk factor (defined in section 9.3.1) for progression to severe COVID-19 at baseline.

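### Table 1 computes age on the index date from calendar years alone, so anyone with a later birthday is recorded one year too old; a few 59-year-olds gain the age risk factor and some may enter EAS wrongly

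*Protocol*

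**What the plan says.** The Age row of Table 1 (protocol section 9.3) describes the variable as "Age on index date" and then fixes it as "Age = Year of index date - Birth year". The row gives age the role of demographic variable and subgroup identifier, and ends with a pointer: "See section 9.3.1 Risk factors for more detail".

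Three other rules use age:

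- **Eligibility** (Abstract, repeated in section 9.2): "Chinese patients aged ≥ 18 years on index date".
- **Risk factor** (section 9.3.1): "Older age (e.g., age \geq 60 years". Section 9.7.1 admits a patient from EAS1 to EAS if illness was mild or moderate at baseline and the patient "had at least one risk factor (defined in section 9.3.1) for progression to severe COVID-19 at baseline". Risk factors also define subgroups in section 9.7.4.
- **eGFR** (Table 1, renal results): age is the exponent of 0.993 in the CKD-EPI equation.

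All index dates fall in one calendar year, since the inclusion criterion in section 9.2 reads: "Patients initiated and took at least one dose of nirmatrelvir/ritonavir between 11 February 2022 and 31 August 2022 during hospitalization". The protocol gives no other definition of age and no correction for birthdays later in the year.

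**The concern.** The label and the formula in the same table cell disagree. Age on a date is normally the number of completed years on that date. Year minus year ignores month and day and gives the age the patient reaches by the end of 2022. The two agree only if the birthday falls on or before the index date. Neighbouring Table 1 variables, such as time since first symptom, are computed from full dates, so the year-only shortcut is particular to age.

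The error goes one way. The formula never understates age and never overstates it by more than one year, so it does not average out. What is at stake is the membership of the age risk group and, through it, of EAS, which is meant to hold patients with a genuine risk factor. The eligibility limit at 18 is exposed in the same way if the formula is used for screening.

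**Working it through.** The protocol states no figure for this error, so there is none to reproduce.

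**Inputs from the protocol.** Index window 11 February to 31 August 2022 (202 days); planned size about 1000; age cuts at 18 and 60; 500 patients planned for the mild or moderate, at-risk set (Table 5).

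**Assumptions, not in the protocol.** Birthdays uniform over the year; index dates uniform over the window for the central figure, with the first and last day as bounds; 1% to 2% of patients born in 1962.

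**Step 1: share recorded one year too old.** For index date d, the share is (days from d to 31 December 2022) / 365.

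| Index date | Calculation | Share |
|---|---|---|
| 11 February | 323/365 | 88.5% |
| 31 August | 122/365 | 33.4% |
| Mean over the window | ((323 + 122)/2)/365 = 222.5/365 | 61.0% |

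Enumerating every pair of birthday and index date gives the same 61.0%. The figure depends on when patients were treated: index dates spread over March to May give 71%, over June to August 46%. Since each error is exactly one year, mean age is overstated by about 0.61 years under the uniform assumption.

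**Step 2: the cut at 60.** Only patients born in 1962 can be misplaced, because 2022 − 1962 = 60 whatever the birthday.

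- Central: 10 × 0.610 = 6.1 to 20 × 0.610 = 12.2, so about 6 to 12 patients who are really 59.
- Bounds: 10 × 0.334 = 3.3 to 20 × 0.885 = 17.7, so about 3 to 18.

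**Step 3: wrong entries into EAS.** A mislabelled patient enters EAS wrongly only if he or she is in EAS1, has mild or moderate illness, and has none of the other factors in section 9.3.1. If 20% to 50% of the mislabelled meet these conditions (assumption), the central range becomes 6.1 × 0.20 = 1.2 to 12.2 × 0.50 = 6.1 patients. That is about 1 to 6 of 500, or 0.2% to 1.2%.

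**Step 4: effect on an EAS proportion.** The shift equals the share of wrong entries times the difference in risk. As an extreme case, let all 18 enter (18/500 = 3.6%) and let their risk differ by 5 percentage points (assumption). The shift is 0.036 × 5 = 0.18 percentage points. The planned half width for 500 patients is 3.50 points (Table 5, at a proportion of 20%; 1.96 × √(0.2 × 0.8/500) = 3.506%).

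**Step 5: the cut at 18.** Everyone born in 2004 gets age 18 from the formula. By Step 1, about 61% of them (33% to 88%) would be 17 on the index date. The protocol gives no basis for the number of such patients.

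**Step 6: eGFR.** One extra year multiplies the computed value by 0.993, a reduction of 0.7%.

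**The case against.** The strongest reply is that the consequences are slight. The study is descriptive with no hypothesis test, effectiveness is secondary, and the primary safety analysis uses all eligible patients, so the cut at 60 does not touch its population. Section 9.3.1 lists many common risk factors, and most people near 60 may qualify through one of them. The age limit is itself given there as an example. Year-only age may also be a privacy measure, because section 9.4 bars the abstraction of personal identification information.

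Most of this stands as a limit on size. The privacy argument explains the choice but does not cure it: the protocol does not offer it as a reason, and a site can enter an integer age without releasing a birth date.

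A reader might infer that the protocol admits 17-year-olds. The text does not establish that. The eligibility criterion is a sentence of its own whose plain meaning is completed age, Table 1 does not give its age variable an eligibility role, and site staff work from the full medical record. Admission of minors follows only if the Table 1 formula is used for screening. Section 7 records approval for adults, so treated 17-year-olds are probably rare.

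A reader might also take the 61% as a rate of misclassification. It is the share whose recorded age is one year high under two uniformity assumptions; away from the cut-offs that year changes no age-threshold classification.

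**Conclusion.** The point holds as a minor error in an operational definition. The formula does not give what its label says, the discrepancy is always upward, and nothing elsewhere in the protocol corrects it. Applied as written, it places some 59-year-olds in the group aged 60 or over: about 6 to 12 patients, range 3 to 18, if 1% to 2% of 1000 were born in 1962. Only a fraction of these would enter EAS wrongly.

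The documents do not support a reading that EAS results are materially biased. Even the extreme case above moves a proportion by about 0.2 percentage points. The eGFR effect is negligible except for a value lying just at a category limit. On eligibility, the finding is an ambiguity: the protocol does not say whether the criterion is checked with the Table 1 formula or with the full date of birth.

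**What to change.** In the Age row of Table 1, define age as completed years on the index date. Have the site compute it from the date of birth in its own records and enter only the integer in the eCRF. State that this value serves the eligibility limit at 18, the risk factor at 60 and the eGFR equation.

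The cost is one line in Table 1 and one eCRF field, with no additional identifier leaving the site. It is best settled before data collection starts (planned for 6 March 2023): if only the birth year is captured, the error cannot be corrected at analysis without going back to the sites. If the year-only rule has to stay, name it as a limitation in section 9.9, require eligibility to be checked against the full date of birth, and add a sensitivity analysis for EAS that does not count age as a risk factor for patients born in 1962.

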COVID-19 severity	Secondary endpoint (effectiveness)	HIS	The first occurrence of severe or critical COVID-19 illness after initiation of nirmatrelvir/ritonavir treatment during observation period, and the date of this first occurrence will be abstracted. ²⁵ COVID-19 severity will be categorized into four levels. Apart from categories of severity level, names of the severity scale used and the relevant parameters used for severity assessment will also be

Table 1. List of variables and operational definitions

Variable	Role	Data source(s)	Operational definition
			abstracted from medical records. See section 9.3.2 COVID-19 Severity for categorization and parameters.
Death	Secondary endpoint (effectiveness)	HIS	Information on cause of death and the date of death will be abstracted.
Time to alleviation of all targeted COVID-19 signs and symptoms	Secondary endpoint (effectiveness)	HIS	Information on alleviation (yes/no) and severity level (if available, including absent, mild, moderate, and severe ²⁰) of each targeted sign/symptom of COVID-19 by date during the observation period will be abstracted from medical records. For a list of targeted signs and symptoms of COVID-19, see section 9.3.3 Signs/symptoms of COVID-19. For the definition of alleviation and the calculation of the time to alleviation, see section 9.3.7. Time to alleviation of all targeted COVID-19 signs and symptoms
Time to two consecutive negative SARS-CoV-2 test results / CT \geq 35	Secondary endpoint (effectiveness)	HIS/LIS	Medical records of dates, time and results of SARS-CoV-2 tests (positive/negative and CT values) after index date will be abstracted. See section 9.3.8 for calculating the time to two consecutive negative SARS-CoV-2 test results / CT \geq 35
Date of admission			As recorded in medical record.
Date of discharge from hospital			As recorded in medical record.

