9.7.3.2. Analysis of effectiveness endpoints

The analyses of effectiveness endpoints will be based on EAS1 and EAS, and the following will be presented:

Proportion of patients with COVID-19 disease severity (described in section 9.3.2) progressed or death from any cause and corresponding 95% CI will be summarized.

Time to alleviation of all targeted COVID-19 signs and symptoms (described in section 9.3.7) will be summarized by K-M plots with the median time and corresponding 95% CI.

Number and percentage of patients with two consecutive negative SARS-CoV-2 test results / CT \geq 35 (specimens collected in two different calendar days) and corresponding 95% CI will be summarized for the patients with at least two SARS-CoV-2 tests after treatment initiation.

Time to the first negative SARS-CoV-2 test result / CT \geq 35 from two consecutive negative SARS-CoV-2 test results / CT \geq 35 (specimens collected in two different calendar days) among patients with at least two SARS-CoV-2 tests (described in section 9.3.8) will be summarized and plotted in a K-M curve with the median time and corresponding 95% CI.

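### Table 1 defines the severity event without reference to baseline, so EAS1 patients already severe or critical at index could be counted as progressed without worsening

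*Protocol*

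**What the plan says.** Section 9.7.3.2 of the protocol sets the analysis: "Proportion of patients with COVID-19 disease severity (described in section 9.3.2) progressed or death from any cause and corresponding 95% CI will be summarized". Section 9.1.2 lists the same endpoint. The section 9.3.2 it refers to describes four categories (mild, moderate, severe, critical) but gives no rule for when a patient has moved between them.

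The operational rule is in Table 1 of section 9.3, in the effectiveness row for COVID-19 severity: "The first occurrence of severe or critical COVID-19 illness after initiation of nirmatrelvir/ritonavir treatment during observation period". The date of that first occurrence is to be abstracted with it. The row adds that "COVID-19 severity will be categorized into four levels" and that the scale used and its parameters are collected.

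On populations, section 9.7.3.2 states: "The analyses of effectiveness endpoints will be based on EAS1 and EAS, and the following will be presented". Section 9.7.1 defines the two sets. For the larger: "The EAS1 will include all patients from FAS who had at least one of the effectiveness variables collected", with a further condition on a recent positive test. For the smaller: "The EAS is a subset of EAS1 and will include patients who had mild or moderate COVID-19 illness at baseline", with at least one risk factor. Only the smaller set restricts severity. Eligibility in section 9.2 does not: "Patients had documented confirmed symptomatic COVID-19 with positive SARS-CoV-2 test in any specimen collected prior to or at initiation of nirmatrelvir/ritonavir". The sole exclusion is participation in an interventional COVID-19 trial.

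**The concern.** The analysis section names a change (severity progressed). Table 1 names a state (severe or critical at some time after the first dose). The two agree for patients who start mild or moderate and then become severe or critical, but can diverge for anyone who is severe or critical at index. Such patients can enter EAS1, and the protocol foresees them: baseline severity uses the four-level scale, section 9.7.4 lists baseline severity as an effectiveness subgroup, and section 9.9 warns that these inpatients could be more severely ill.

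At stake is the meaning of the EAS1 progression proportion. Two analysts working from this text could classify the same patients differently. The EAS1 and EAS proportions would then differ partly because of the event rule, not only because the populations differ.

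**Working it through.** **What the protocol computes.** It gives no expected rate or precision for the progression endpoint. Table 5 concerns the viral-clearance proportion: 1.96 × √(0.20 × 0.80 / 800) = 2.77%, as stated, and 1.96 × √(0.20 × 0.80 / 500) = 3.51% against 3.50% stated, a trivial rounding difference. It supplies only a working size for EAS1 below.

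**The possible readings, by baseline category**

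| Course after index | Table 1 read literally | Table 1 read as new onset | Ordinary sense of *progressed* |
|---|---|---|---|
| Mild or moderate, becomes severe or critical | event | event | event |
| Severe, stays severe | event | no event | no event |
| Severe, becomes critical | event, dated at the first severe or critical record | no event | event |
| Critical, stays critical | event | no event | no event |
| Death | event | event | event |

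The first and last rows agree. The middle rows can occur in EAS1 but not in the EAS.

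**Inputs for the size.** Let b be the share of EAS1 severe or critical at baseline, and p the true rate of progression or death in the remaining patients. The protocol gives neither. I assume b from 1% to 10% and p from 1% to 5%, with 3% as the main case.

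**Literal reading.** If every baseline severe or critical patient has a qualifying record after dosing, the reported proportion is b + (1 − b)p. This is an upper limit, because each such patient can add at most one event.

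| b | p = 1% | p = 3% | p = 5% |
|---|---|---|---|
| 0 | 1.00% | 3.00% | 5.00% |
| 1% | 1.99% | 3.97% | 5.95% |
| 5% | 5.95% | 7.85% | 9.75% |
| 10% | 10.9% | 12.7% | 14.5% |

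For example, 0.05 + 0.95 × 0.03 = 0.0785. The excess over p is b(1 − p): at p = 3% it is 0.97, 4.85 and 9.70 percentage points for b of 1%, 5% and 10%.

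**New-onset reading.** Baseline severe or critical patients contribute only through death. If none die, the proportion is (1 − b)p: at p = 3% it is 2.97%, 2.85% and 2.70% for the same b. The figure is slightly diluted, and worsening from severe to critical is left out.

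**Precision if the severity part is restricted to mild or moderate patients.** Taking Table 5's 800 as the size of EAS1 (an assumption, since that row does not mention the recent-test condition), b of 1%, 5% and 10% leaves 792, 760 and 720 patients. At p = 3% the half widths, 1.96 × √(0.03 × 0.97 / n), are 1.19, 1.21 and 1.25 points, against 1.18 with 800. Little is lost.

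**The case against.** The strongest reply is that the endpoint already says *progressed*, and a patient severe before and after dosing has not progressed. Table 1 describes what is abstracted, *first occurrence* can mean new onset, and section 9.7 leaves detailed methods to a SAP that is not shown. Baseline severity is collected on the same four-level scale, so a comparison with baseline is possible. Baseline-severity subgroups are listed, and the approved indication in section 7 is mild-to-moderate illness, so few patients may be affected.

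Much of this stands. A reader might infer that EAS1 will certainly report baseline severity as progression, or that the rate will be inflated by some fixed multiple. The protocol supports neither: its wording allows a reading in which unchanged patients are not events, and any multiple rests on assumed b and p. Nor does it follow that the EAS1 figure is worthless, since deaths and new progression are included.

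The rest of the reply does not remove the problem. No passage ties the event to the baseline category. The new-onset reading has its own gap, because no separate date of reaching critical illness is named for a patient already severe. A SAP can choose a derivation but cannot be relied on to recover a date that sites were not asked to record. The subgroup analyses depend on adequate data and would not correct the pooled EAS1 figure.

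**Conclusion.** The point holds as an unreconciled definition within the protocol, confined to the progression proportion in EAS1. Patients severe or critical at index could be counted as events without worsening, or kept in the denominator with death as their only possible event; the text does not choose. With p assumed at 3% and b between 1% and 10%, the literal reading gives at most about 4% to 13%, while the new-onset reading stays just under 3% if none of these patients die. Both b and p are assumptions, and the bias is zero if no such patient enters EAS1.

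The EAS result is protected, and the primary safety objective and the study-size calculation are untouched. For a secondary endpoint in a single-arm descriptive study, this should be fixed, preferably before abstraction begins, because Table 1 determines what sites record.

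**What to change.** Reconcile Table 1 with section 9.7.3.2. Define the event as reaching, after index, a severe or critical category that is worse than the patient's baseline category, or death from any cause. This also settles that a move from mild to moderate alone is not an event, which the word *progressed* leaves open.

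Abstract the first post-index date of severe illness and the first post-index date of critical illness as separate fields. Report the EAS1 proportion by baseline severity as a fixed output, not one conditional on adequate data. A simpler alternative is to restrict the severity component in EAS1 to patients mild or moderate at baseline and report death separately for the rest.

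The cost is revised wording in two places, one extra eCRF date and one extra table. No additional patients are needed, and baseline severity is already collected.
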